## 12. Secondary Endpoint (ITT and ITT age subgroups)

For secondary endpoints that test proportion:

- Deaths are always counted as worst case (i.e. deaths are counted as being hospitalized through Day 28).
- Missing data is analyzed in two ways:
  - Missing data is excluded after date of last follow-up. i.e. any analysis after the date of last follow up will exclude the missing subject from the denominator. This represents the “best case” for the missing data.
  - Missing data is assigned the worst case. i.e. for hospitalization, this missing data would be assumed to be hospitalized through Day 28. This represents the “worst case” scenario for the missing data.

For secondary endpoints that are time to events, the Fay-Shaw method accounts for deaths and missing data. In cases where the Fay-Shaw method is not appropriate, the Log-Rank p-value will be reported.

- Percent hospitalized at Study Day 3, 7, 14 and 28 [14.2.3.2.x]
  - Table N (%) hospitalized at Study Day 3, 7, 14 and 28 and test of proportions
  - Figure of proportions at each time point
- Duration of clinical symptoms [14.2.4.1.x]  
Subjects with 0-1 on all symptoms on Day 0 are considered to have a time of 0 hours.
  - Table: time (in hours) from symptom onset to symptom free (symptom free is 0-1 on all symptoms that last at least 2 days), noting min, 25%tile, 50%tile, 75%tile
    - P-value obtained using Shaw-Fay method (here only treat deaths as worst rank and missing as censored)
  - Figure using Kaplan-Meier plot.
- Duration of fever- defined as temperature  $\geq 38.0$  C [14.2.4.2.x]
  - Table: v with min, 25%tile, 50%tile, 75%tile, max.
    - P-value obtained using Shaw-Fay method (here only treat deaths as worst rank and missing as censored)

- Figure using Kaplan-Meier plot.
- Use of supplemental oxygen (or increase greater than baseline oxygen requirement) [14.2.5.1.x]
  - Resolution is defined as off oxygen. Subjects without stop date will be censored at 28 days. A time of 00:00 will be imputed for subjects with a stop date but missing stop time.
  - Table N (%) of use of oxygen (Y/N) at any point during the study, and at each time point
    - P-value obtained using test of proportions
  - Figure of proportions at each time point
  - Table duration of oxygenation: defined as time of oxygen first administered, to time off oxygen (in hours) noting min, 25%tile, 50%tile, 75%tile, max [14.2.5.2.x]
    - Table includes all subjects – where subjects not requiring oxygen have 0 hours.
    - P-value obtained using Shaw-Fay method (here only treat deaths as worst rank and missing as censored)
  - Table duration of oxygenation: defined as time of oxygen first administered, to time off oxygen (in hours) noting min, 25%tile, 50%tile, 75%tile, max [14.2.5.3.x]
    - Table is restricted to those requiring oxygen at any point during the study.
    - P-value obtained using Shaw-Fay method (here only treat deaths as worst rank and missing as censored)
  - Figure using Kaplan-Meier plot
    - Figure includes all subjects – where subjects not requiring oxygen have 0 hours.
    - Figure is repeated, but restricted to those requiring oxygen at any point during the study.
- Admission to ICU
  - Table N (%) of requiring ICU (Y/N) at any point during the study, and at each time point [14.2.6.1.x]
    - P-value obtained using test of proportions
  - Figure of proportions at each time point
  - Table duration of ICU: defined as time subject admitted to ICU, to time discharged from ICU (in hours) noting min, 25%tile, 50%tile, 75%tile, max [14.2.6.2.x]
    - Table includes all subjects – where subjects not requiring ICU have 0 hours.
    - P-value obtained using Shaw-Fay method (here only treat deaths as worst rank and missing as censored)
  - Table duration of ICU: defined as time subject admitted to ICU, to time discharged from ICU (in hours) noting min, 25%tile, 50%tile, 75%tile, max [14.2.6.3.x]
    - Table is restricted to those requiring ICU at any point during the study.
    - P-value obtained using Shaw-Fay method (here only treat deaths as worst rank and missing as censored)
  - Figure using Kaplan-Meier plot
    - Figure includes all subjects – where subjects not requiring ICU have 0 hours.
    - Figure is repeated, but restricted to those requiring ICU at any point during the study
- Intubation/mechanical ventilation
  - Table N (%) of requiring mechanical ventilation (Y/N) at any point during the study, and at each time point [14.2.7.1]

- P-value obtained using test of proportions
- Figure of proportions at each time point
- Table duration of mechanical ventilation: defined as time subject placed on mechanical ventilation, to time extubated (removed from mechanical ventilation) noting min, 25%tile, 50%tile, 75%tile, max [14.2.7.2.x]
  - Table includes all subjects – where subjects not requiring mechanical ventilation have 0 hours.
  - P-value obtained using Shaw-Fay method (here only treat deaths as worst rank and missing as censored)
- Table duration of mechanical ventilation: defined as time subject placed on mechanical ventilation, to time extubated (removed from mechanical ventilation) noting min, 25%tile, 50%tile, 75%tile, max [14.2.7.3.x]
  - Table is restricted to those requiring mechanical ventilation at any point during the study.
  - P-value obtained using Shaw-Fay method (here only treat deaths as worst rank and missing as censored)
- Figure using Kaplan-Meier plot
  - Figure includes all subjects – where subjects not requiring mechanical ventilation have 0 hours.
  - Figure is repeated, but restricted to those requiring mechanical ventilation at any point during the study
- Proportion of subjects who develop complications including pneumonia, acute respiratory distress syndrome (ARDS), sepsis, or bronchiolitis at Day 3, 7, 14 and 28
  - Table for any complication: restricted to those subjects without any at baseline [14.2.8.1.x]
  - Figure of proportions at each time point
  - Table for each complication: restricted to those subjects without that complication at baseline [14.2.8.2.x]
    - Pneumonia
    - Respiratory failure requiring mechanical ventilation
    - ARDS
    - Sepsis
    - Bronchiolitis
  - Figure of proportions at each time point
- Global assessment [14.2.9.x]
  - Table duration (days) from enrollment until stating the first affirmative to global assessment questions
    - P-value obtained using Shaw-Fay method (here only treat deaths as worst rank and missing as censored)
  - Figure using Kaplan-Meier plot (time until stating the first affirmative).
  - There are two global assessment questions for adults and two global assessment questions for children. Each of these four questions will be analyzed separately.
- Antibiotic/antiviral use during hospitalization [14.2.10]

- Table N (%) of subjects with an antibiotic starting on or after Day 3
  - P-value obtained using test of proportions
- Systemic steroids use during hospitalization [14.2.10]
  - Table N (%) of subjects with systemic steroids starting after Day 3
    - P-value obtained using test of proportions
- Re-hospitalization within 28 days [14.2.10]
  - Table N (%) of subjects with rehospitalization within 28 days
    - P-value obtained using test of proportions
  - Listing of rehospitalizations: Randomized arm, days from randomization to re-hospitalization, subject ID, site, age, (sort by randomized arm, day from randomization)
- Evaluate the virologic efficacy of NTZ + SOC vs. PCB + SOC with regards to:  
Restricted to those with virus detectable on Day 0
  - Table N (%) of subjects that had any virus detectable on Day 0, and no longer had any virus detectable on Day 3 [14.2.11]
    - If more than one virus was present on Day 0, both viruses must be cleared to be considered as no detectable virus. If Day 3 has a virus that was not detected on Day 0 (day 0 had virus A and Day 3 virus B), this is not considered as having no detectable virus.
    - P-value obtained using test of proportions
  - Table N (%) of subjects that had virus detectable on Day 0, and had a different virus detectable on Day 3.

## Appendix 1

The primary endpoint is time to hospital discharge or death within 28 days. The primary analysis will follow the intent to treat principal where all patients randomized will be used in the analysis and analyzed according to treatment assignment. Observations will be censored at 28 days if discharge or death does not occur before 28 days.

The Shaw-Fay methodology uses ranks to form the test statistic. The following ranking system will be followed if no loss to follow up occurs. Patients who die will be given worse ranks than those who are alive. Among those who die, early deaths receive worse ranks than those who are alive and among those alive the order of ranking from worst to best is no discharge, late, than early discharge. Table 1 gives an example of rankings for an invented data set.

Table 1. Example of rankings for invented data set. C indicates censored at day 28 or censored due to death. Larger ranks are worse than smaller ranks.

Person	Day of discharge	Day of Death	Rank
1	C	5	8
2	C	10	7
3	3	15	6
4	C	C	5
5	15	C	4
6	5	C	3

7	2	C	1.5
8	2	C	1.5

The test statistics is the sum of the ranks for patients in the Nitazoxanide group. Treatment labels will be permuted to calculate the probability of obtaining a test statistic as extreme as the observed sum of the ranks of the experimental group.

If patients are lost to follow up (i.e. withdraw consent) prior to day 28 the Shaw-Fay formulation of the 2 sample Mann-Whitney Wilcoxon rank-sum statistic will be formed. Ranks for observed data will be as described above and ranks for those with missing data will be as described in Shaw-Fay. R code will be provided that calculates the ranks for those patients who are lost to follow up. The rank based permutation test as described above will be used to calculate the test statistics.

Reference: Shaw, Pamela A., and Michael P. Fay. "A rank test for bivariate time-to-event outcomes when one event is a surrogate." *Statistics in Medicine* 2016; 35(19): 3413-3423.

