## 11. Primary Endpoint (ITT, ITT age subgroups, ITT pediatric formulation subgroups, ITT virology subgroups)

Table to show the completeness of the primary endpoint should include number (%) with [14.2.2]:

- Complete data (Day of hospitalization and discharge or death)
- Incomplete data (missing day of hospitalization or discharge/death)

The following table and figure provide descriptive statistics of the primary endpoint. The table and figures should impute values of 28 days for patients who died and should censor patients with missing discharge date at the time of last follow up.

- Figure: Kaplan-Meier plot of time to hospital discharge/death (only ITT and ITT age subgroups)
- Table: with the following estimates from the Kaplan-Meier curves- 25th, 50th and 75th percentile along with min and max values in hours [14.2.3.1.x]

- The between group difference in median time to discharge will be used to estimate the treatment effect and will be reported along with a 95% two-sided confidence interval.
- Additionally, data from median, min, max converted to “days, hours”
- The p-value for the 2 group comparison of the primary endpoint analysis will be performed using the Shaw-Fay method as described in appendix 1.
- Sensitivity analyzes to exam effect of missing death or discharge data. (only ITT and ITT age subgroups)
  - Figure with Kaplan-Meier curves and Shaw-Fay p-values on the ITT only where missing death or discharge dates are imputed in the placebo group as censored at the time of last follow up and in the experimental group are imputed as events at day 28.
  - Figure with Kaplan-Meier curves and Shaw-Fay p-values on the ITT only where missing death or discharge dates are imputed in both groups as events at day 28.
  - For any imbalance seen in baseline characteristics ( $p < .05$ ) perform a cox proportional hazards model with deaths receiving event times of 28 days. Missing discharge dates will be censored at last follow up time.

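### SAP section 12 counts every death as worst case in all secondary proportions, with no date limit or exempted endpoint; read literally, this overwrites observed outcomes and reports composites with death under single-event names

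*SAP*

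**What the plan says.** SAP section 12 opens its general rules with "For secondary endpoints that test proportion". The first rule under that heading is "Deaths are always counted as worst case (i.e. deaths are counted as being hospitalized through Day 28". Missing data then get two analyses. One drops the subject from the denominator after last follow-up. The other reads "Missing data is assigned the worst case. i.e. for hospitalization, this missing data would be assumed to be hospitalized through Day 28". Deaths get one treatment only.

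The endpoint bullets that follow do not mention death. Among them are "Table N (%) of subjects with rehospitalization within 28 days", "Table N (%) of subjects with systemic steroids starting after Day 3" and, for virology, "Table N (%) of subjects that had any virus detectable on Day 0, and no longer had any virus detectable on Day 3". Each of these is compared by a test of proportions, as are antibiotic starts and the yes/no tables for oxygen, ICU and ventilation. Complications are also reported as proportions.

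For the primary endpoint, SAP section 11 says "The table and figures should impute values of 28 days for patients who died". Protocol section 9.2 likewise keeps deaths in hospital at Day 28 in the Kaplan-Meier curves. The ranking example in SAP Appendix 1 includes a patient (person 3) discharged on Day 3 who dies on Day 15.

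**The concern.** For percent hospitalised, the worst case is defined. For the other proportions it is not, and the natural meaning is that the unfavourable event happened. A programmer following the text would then do three things:

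- Count a patient who died in the first admission as re-hospitalised, and as having started antibiotics or steroids, whatever the record shows.
- Recode a negative Day 3 swab as not cleared because of a death days or weeks later.
- Print the results under the names of the single events, although each has become a composite with death.

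The first is also incoherent. A patient deemed hospitalised through Day 28 was never discharged and cannot be readmitted. At stake is interpretation: a mortality difference could appear as an effect on re-hospitalisation, steroid use or viral clearance, and a real effect on one of these could be diluted by deaths common to both arms. No as-observed analysis of deaths is planned as a check.

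**Working it through.** **No planned figure to reproduce.** The documents give no expected rate or power for the secondary proportions. Protocol section 9.2 bases the sample size (258, raised to 290) on hospital days alone and says secondary endpoints may not be adequately powered. The planning data were survivors with stays under 28 days, so they give no mortality. The 4% mentioned there is data removed by truncation, not a death rate.

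**Scope of the rule.** The heading covers all secondary proportions, and the rule says *always*. The parallel missing-data rule names hospitalisation as an illustration of a general worst case. This suggests that the hospitalisation clause in the death rule is also an example and not a limit.

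**Effect in the SAP's own example (Appendix 1, eight persons), number counted as hospitalised:**

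| | Day 7 | Day 14 | Day 28 |
|---|---|---|---|
| Death always worst case | 5 | 5 | 4 |
| Death counted only from its date | 4 | 4 | 4 |

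The difference is person 3, who was alive and discharged on Days 7 and 14.

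**Effect on an event proportion.** Let p be the true event rate and d the death rate, both assumed, and independent of each other.

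- Reported rate = p(1 − d) + d
- Share of counted events that are deaths without the event = d(1 − p) / reported rate

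With p = 5%:

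| d | Reported rate | Share |
|---|---|---|
| 2% | 0.05 × 0.98 + 0.02 = 6.9% | 0.019 / 0.069 = 28% |
| 4% | 0.05 × 0.96 + 0.04 = 8.8% | 0.038 / 0.088 = 43% |
| 8% | 0.05 × 0.92 + 0.08 = 12.6% | 0.076 / 0.126 = 60% |

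If no patient has both outcomes, the share is d/(p + d) = 29%, 44% or 62%. Positive overlap gives less than the table. With commoner events the share falls: for the same death rates it is 15%, 26% or 42% at p = 10%, and 7%, 14% or 24% at p = 20%.

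**Effect on the test.** With 290/2 = 145 per arm, a two-sided 0.05 level and the normal approximation, power = Φ[(|Δ| − 1.96·SE₀)/SE₁], where SE₀ is the pooled and SE₁ the unpooled standard error.

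- No effect on the event (5% in both arms), deaths 8% vs 3%: recoded rates 12.6% vs 7.85%, Δ = 0.0475, SE₀ = 0.0356, SE₁ = 0.0355. The test rejects with probability about 27%. With deaths of 5% vs 2% it is about 14%, and with 10% vs 3% about 44%.
- True effect 15% vs 5%, equal deaths of 0, 2%, 5% or 10%: power is 81%, 74%, 63% or 50%.
- Day 3 viral persistence 50% in both arms, deaths 8% vs 3%: 0.5 × 0.92 + 0.08 = 54.0% vs 0.5 × 0.97 + 0.03 = 51.5%, a spurious 2.5 points. This treats every death as recoded. Deaths before the swab may reasonably count as failures, so the part due to overwritten swabs is smaller.

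**The case against.** The strongest reply is that the SAP nowhere states these recodings. It spells out one consequence of death, hospitalisation through Day 28. The re-hospitalisation table comes with a listing of days to re-hospitalisation, which a first-admission death cannot supply, and viral clearance is defined by the two swabs alone. A reader might infer that the sponsor has announced a plan to count deaths as re-hospitalisations, steroid starts and viral failures. The documents do not support that; it follows only from applying the general rule literally. But if the narrower reading was meant, the SAP has no rule for deaths in the other proportions, and someone must choose one. The text needs amending either way.

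A reader might also infer that percent hospitalised is handled wrongly. That does not stand. The rule agrees with the primary Kaplan-Meier display and with the Appendix 1 ranking, where any death ranks below any survivor, and it is a defensible composite. It displaces observed status only for patients who die after discharge.

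Nor is every secondary endpoint touched. Durations and global assessment have their own Shaw-Fay handling of deaths. Mortality is also reported separately in SAP section 7, which, with the re-hospitalisation listing, lets a careful reader separate death from that event. Steroid and antibiotic starts and viral clearance have no such listing in section 12.

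**Conclusion.** The point holds as a defect in the wording of one rule, limited to the secondary proportions. Taken literally, the rule replaces observed outcomes, contradicts itself for re-hospitalisation, and labels composites with death as single events. Taken narrowly, it leaves those endpoints without a rule.

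The size cannot be fixed from the documents. At an assumed 5% event rate and 2% to 8% deaths, 28% to 60% of counted events would be deaths without the event. The share is lower for commoner events, for positive overlap between event and death, and if deaths are few. The false signal arises only if mortality differs between arms; equal mortality dilutes instead. The primary test and the sample size are unaffected. The change is worth making, but it does not threaten the trial's main conclusion.

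**What to change.** Amend SAP section 12 to state, for each proportion, what a death counts as:

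- **Event proportions** (re-hospitalisation, ICU, ventilation, oxygen, complications, antibiotic or steroid start): report the observed N (%) and, beside it, a row labelled *event or death*.
- **Day 3 viral clearance:** use the actual swab whenever it was taken, and apply the worst case only to deaths before the swab.
- **Percent hospitalised:** the worst-case rule may stay, for consistency with the primary analysis. Label the row *hospitalised or died by Day 28*, and add observed status at Days 3, 7 and 14 for patients discharged before they died.

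The cost is SAP wording and one extra row per table. No new data are needed.

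### Oxygen, ICU and ventilation durations are given p-values in ever-user subsets that treatment can change; as a lesser point, symptom duration uses two time origins.

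*SAP*

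**What the plan says.** **Support durations.** For each of oxygen, ICU and ventilation, SAP section 12 plans three comparisons.

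- A test of proportions for any use: "Table N (%) of use of oxygen (Y/N) at any point during the study", "Table N (%) of requiring ICU (Y/N) at any point during the study" and "Table N (%) of requiring mechanical ventilation (Y/N) at any point during the study".
- A duration table in all subjects, with 0 h for those who never needed the support, and a Shaw-Fay p-value.
- A second duration table, also with a Shaw-Fay p-value, in ever-users only: "Table is restricted to those requiring oxygen at any point during the study" (14.2.5.3), "Table is restricted to those requiring ICU at any point during the study" (14.2.6.3) and "Table is restricted to those requiring mechanical ventilation at any point during the study" (14.2.7.3). A restricted Kaplan-Meier figure goes with each.

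Protocol section 3.2 names ICU and oxygen requirements among the outcomes NTZ is expected to improve. Section 2.2 makes all three supports secondary objectives.

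**Symptom duration.** The same SAP section defines this as "time (in hours) from symptom onset to symptom free", where symptom free means scores of 0–1 on all symptoms lasting at least two days. It adds: "Subjects with 0-1 on all symptoms on Day 0 are considered to have a time of 0 hours". SAP section 3 tabulates the interval from onset to randomisation, so the plan itself expects onset to come before Day 0.

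**The concern.** Randomisation makes the arms comparable as whole groups, or within subsets fixed before treatment. Ever needing oxygen, ICU or ventilation is neither. If NTZ spares the milder patients from support, those left in its ever-user group are sicker on average and stay on support longer, even though the drug lengthened nobody's support. The report could then show a significantly longer duration on NTZ beside an all-subject test that favours NTZ, and the SAP does not say which of the two leads. The SAP's own complications tables avoid this, because they restrict by status at baseline.

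For symptom duration, a value of 0 h makes sense only if the clock starts at Day 0, yet everyone else's clock starts at onset. The percentiles and the Kaplan-Meier curve therefore place two different quantities on one axis.

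**Working it through.** The plan has no power or rate figure to reproduce for these endpoints. Protocol section 9.2 sizes the trial on the primary endpoint only. The documents supply 290 / 2 = 145 per arm; the rest are assumptions. All simulations use a two-sided 0.05 tie-corrected Wilcoxon rank-sum test, with no deaths or censoring.

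**1. Ever-user test**

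Model: latent severity S is standard normal, and support is needed if S > c, where c = Φ⁻¹(1 − p) and p is the proportion needing it. Log duration = log 4 + 0.7(ρS + √(1 − ρ²)E), with E an independent standard normal and durations in days. The duration distribution is the same in both arms, so treatment changes only who needs support.

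Hand check, need 50% versus 31%, ρ = 0.7:

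- Expected ever-users: 145 × 0.50 = 72.5 and 145 × 0.31 ≈ 45.
- Mean severity among users, λ = φ(c)/p: 0.399/0.50 = 0.798 (c = 0) and 0.353/0.31 = 1.138 (c = 0.496).
- Difference in mean log duration: 0.7 × 0.7 × (1.138 − 0.798) = 0.167, a ratio of e^0.167 = 1.18 against NTZ.
- Variance of S among users, 1 + cλ − λ²: 0.363 and 0.269. Variance of log duration, 0.49 × (0.49 × var + 0.51): 0.337 and 0.314.
- SE = √(0.337/72.5 + 0.314/45) = 0.108, so z = 0.167/0.108 ≈ 1.54 and the chance of a significant result against NTZ is Φ(1.54 − 1.96) ≈ 34%.

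Simulation gives 33% at the same setting. The fuller results are:

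| Need, placebo vs NTZ | ρ = 0.3 | 0.5 | 0.7 | 0.9 |
|---|---|---|---|---|
| 50% vs 31%: restricted test rejects | 9% | 15% | 33% | 69% |
| 50% vs 31%: all-subject test favours NTZ | 86% | 83% | 79% | 70% |
| 15% vs 9%: restricted test rejects | – | 6% | 9% | 19% |

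In the first row nearly all rejections go against NTZ. For need falling from 50% to 40–45%, the restricted test rejects about 4–12% at ρ = 0.3–0.7 and 9–26% at ρ = 0.9. With need unaffected it rejects about 5%. With 30% already on support at baseline, 20% new need, and 25–50% of the mildest new need prevented, it rejects 5–12% at ρ = 0.3–0.7 and 9–24% at ρ = 0.9.

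**2. Symptom clock**

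Take two subjects with onset 120 h before Day 0. A is at 0–1 on Day 0; B becomes symptom free 24 h later.

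| Rule | A | B | Difference |
|---|---|---|---|
| SAP | 0 h | 120 + 24 = 144 h | 144 h |
| Randomisation for all | 0 h | 24 h | 24 h |
| Onset for all | 120 h | 144 h | 24 h |

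The cost of mixing is the SAP rule set against a consistent onset clock. Assumptions: median 4 versus 3 days after randomisation, log SD 0.7, independent onset uniform over the preceding 0–5 or 0–7 days, 10% at 0 h.

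- Medians, 0–5 days: 151.9 vs 130.7 h under both rules. For 0–7 days: 178.5 vs 156.1 h (SAP) and 178.5 vs 157.4 h (onset for all).
- Power lost to mixing: about 2–5 points with 10% at 0 h, and under 1 point with 2%.
- Null rejection with 10% at 0 h: 4.2–5.4%.
- Curve: with onset 0–5 days before, it drops 10% at 0 h, then only a further 0.5% by about 36 h (placebo) or 29 h (NTZ).

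**The case against.** The strongest reply on support durations is that the SAP already specifies a test of proportions and an all-subject duration test for each support, and nothing promotes the restricted table above them. That is correct. A reader might infer that the plan has no valid test of support duration; it does. It is also fair that the high rejection rates need a large fall in need together with a strong link between severity and duration, and that subjects already on support at Day 0 enter the subset whatever their treatment. What stands is that a p-value is still attached to a comparison randomisation does not protect, with no caution on reading it.

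On symptoms, a reader might infer three stronger things, and the documents support none of them.

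- **That the test is biased.** Onset time and Day 0 status precede treatment, so type I error holds.
- **That mixing origins shrinks the treatment effect.** Under the same assumptions a 25% reduction already shows as 14.1% (0–5 days) or 12.2% (0–7 days) on an onset clock with nobody at 0 h. The shrinkage belongs to that clock.
- **That the onset clock is itself an error.** The objective is duration of symptoms with no start time fixed, and the supporting trial described in Protocol section 1.2.5 counted from illness onset in its influenza-infected analysis and from first dose in its all-treated analysis. Depending on how time since onset relates to remaining illness, an onset clock can lose or gain power.

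The 10% at 0 h is also an assumption. The share could well be small among patients hospitalised for this illness.

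**Conclusion.** Both points hold, and both are minor. The ever-user p-values for oxygen, ICU and ventilation do not estimate a treatment effect on duration when treatment changes need. The distortion runs from negligible (need unchanged, or a modest fall with a weak severity–duration link) to severe (need 50% to 31% with correlation 0.7–0.9). Its direction is against NTZ if the cases prevented are the mild ones. These figures depend on assumed need, correlation and baseline support, none of which the documents give.

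The symptom definition is internally inconsistent, but the harm is confined to an artificial step at 0 h, a distorted minimum and lower tail, and a few power points if the 0 h group is around 10%. The primary endpoint, its test and the sample size are untouched.

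**What to change.** **Support durations.** State that the all-subject duration tests and the tests of proportions are the inferential analyses. Keep tables 14.2.5.3, 14.2.6.3 and 14.2.7.3 and their restricted Kaplan-Meier figures, without p-values and labelled as descriptive of a subset that treatment may have altered. The cost is three supportive p-values.

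**Symptom duration.** Use one origin for every subject. There are two coherent options, and choosing between them is the sponsor's choice of estimand.

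- **Randomisation.** The 0 h rule then makes sense. Protocol section 6 already sets Day 0 at randomisation, and the SAP runs the global-assessment duration from enrollment. This measures remaining illness and leaves total duration descriptive. If late presenters have clearly less illness left (correlation about −0.5, onset 0–5 days before), it gives up about 4 power points, or 7 with 10% at 0 h.
- **Onset.** This measures total illness. Subjects already symptom free on Day 0 should then get their onset-to-Day-0 time or be reported as a separate count. Protocol section 6.2.1.3 records onset only as a day, so the hours reported would be approximate.

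Both changes are SAP wording and need no new data.
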